The effect of anti-CD14 has been observed in experimental animal and human models. In non-human primates, LPS infusion causes a response that models septic shock. Treatment with two different anti-CD14 mAbs abrogated the systemic effects of LPS infusion with preservation of mean arterial pressure (MAP), reduced circulating cytokine levels, and a relatively preserved lung epithelial permeability barrier (Leturcq et al. 1996). In rabbits, treatment with an anti-CD14 mAb protected against the lethal effects of repeated LPS exposure (Schimke et al. 1998). In a model of Gram-negative pneumonia in rabbits, University of Washington investigators found that treatment with an anti-CD14 mAb protected animals from the systemic effects of localized infections (Frevert et al. 2000). Treated animals had improved MAP and required less intravenous fluid. The treated animals had slower clearance of the bacteria instilled in the lungs, which was not seen in a separate study of bacterial clearance in antibiotic treated rabbits (Axtelle et al. 2003; Verbon et al. 2001). These data show that anti-CD14 treatment can attenuate the adverse systemic effects of Gram-negative infections. More recently, studies in a porcine model of *E. coli* bacteremic sepsis have shown that pre-treatment with a different anti-CD14 monoclonal antibody reduced circulating levels of IL-1 β , IL-6, and TNF α , as well as tissue levels of IL-6 in the lungs, liver, spleen, and kidneys (Thorgersen et al. 2010; 2013). Notably, anti-CD14 did not significantly alter the load of *E. coli* bacteria or LPS measured in lung tissue. LPS levels detected in liver and spleen were higher in the anti-CD14-treated animals suggesting augmented clearance of circulating LPS.

Taken together these preclinical data support using the CD14-blocking antibody, IC14, as a therapeutic intervention in lung injury. Dampening inflammation via transient blockade of CD14 can protect the host from the extreme pro-inflammatory environment present early in the development of lung injury, leading to less severe injury and better clinical outcomes.

1.3. Clinical Studies

[figure not shown]
Human LPS-Challenge Study

In a human model of LPS infusion, researchers showed that pretreatment with IC14 (1 mg/kg i.v.) mitigated the inflammatory effects of intravenous LPS (4 ng/kg i.v.) (Verbon et al. 2001). This phase 1 study showed that IC14 is well tolerated and has anti-inflammatory effects in humans.

Clinical Data in Patients

In a randomized, double-blind, placebo-controlled, dose-ranging, multiple-center, phase 1 trial in patients with severe sepsis, IC14 was administered intravenously to four different groups (n=8/group): 1) single dose of 1 mg/kg, 2) single dose of 4 mg/kg, 3) 4 doses of 4 mg/kg/day, 4) 1 dose of 4 mg/kg on Day 0 followed by 3 doses of 2 mg/kg/day (Reinhart et al. 2004; Axtelle et al. 2003). A placebo arm was included for each group (n=2/group). Single and multiple doses of IC14 were generally well tolerated and did not induce anti-drug antibody formation or increase the incidence of secondary bacterial infections. Participants in the multi-day IC14 groups showed a trend towards reduced multi-organ dysfunction score (MODS) (p=0.06). No significant differences in mortality or inflammatory cytokine production were noted in this small study. One SAE occurred (hypotension and rash) in a treated participant, which resolved with ranitidine, dimetindine, and prednisolone.

An NIH-sponsored double-blind randomized placebo-controlled phase 2 study of 13 critically ill patients supports the use of IC14 to treat lung injury resulting from increased epithelial and endothelial permeability. In this study, IC14 or placebo were administered to critically ill patients with ARDS at the University of Washington (Seattle, WA). Patients with ARDS were randomized to receive either IC14 4 mg/kg/day x 1 day and 2 mg/kg/day x 3 days (n = 7) or placebo for 4 days (n = 6). Bronchoalveolar lavage (BAL) was performed at baseline and again on Days 2-3 and 5-7 to measure leukocyte counts and differentials, total protein, and pro-inflammatory cytokines and chemokines in the BAL fluid. This trial was stopped early because patients were being enrolled in competing trials; nevertheless, the data showed trends for reductions in total and percentage of neutrophils in lung lavage fluid, as well as plasma IL-6 and IL-8, consistent with an improvement in lung and systemic inflammation (Figure 1 below). Notably, the pre-treatment BAL markers of lung inflammation were higher in the IC14-treated participants, suggesting worse lung inflammation at baseline. No IC14-related safety concerns were noted. Taken together, this trial suggests that administration of IC14 is feasible and safe in critically ill patients with ARDS and may reduce markers of inflammation indicative of breakdown of the endothelial and epithelial permeability barrier.

		Day 1 (baseline)	Day 3	Day 7
Plasma IL-6 pg/ml Median (IQR)	IC14	449.8 (42.4-4867.2)	109.5 (42.4-267.3)	90.2 (4.8-108.9)
	Placebo	180.8 (92.8-371.3)	75.3 (42.4-586.0)	319.1 (121.8-516.4)
BALF IL-6 pg/ml Median (IQR)	IC14	1047.6 (227.9-1396.2)	41.6 (25.6-738.3)	23.8 (4.8-45.2)
	Placebo	79.6 (7.0-979.7)	200.4 (13.3-4147.4)	173.6 (21.1-326.1)

Figure 1. IC14 Pilot Trial in ARDS

A phase 2, randomized double-blind study of IC14 in 180 patients with community-acquired pneumonia did not show a significant decrease in incidence of therapeutic failure, but the treatment was well tolerated with no significant increase in TEAEs, SAEs, or secondary infections (ICOS Abbreviated Clinical Study Report 2004).

Previous Phase 1-2 studies with IC14 have documented a favorable safety profile, and it has been generally well tolerated. Mild side effects reported in healthy participants included headaches, rashes and tingling lasting a few hours, runny nose, fever and chills, sleepiness, and light headedness. In patients with severe sepsis, one serious treatment-related adverse event was reported. That subject experienced hypotension and diffuse exanthema which resolved with

administration of ranitidine, prednisolone and dimetindine. None of the 168 subject IC14 exposures has resulted in detectable anti-IC14 antibodies. IC14 has not been associated with an increase in ophthalmologic infiltrates or signs and symptoms of meningeal inflammation in humans. Signs of asymptomatic pleocytosis were noted in preclinical toxicology studies of nonhuman primates administered the antibody. In a phase 2 trial of IC14 for treatment of acute lung injury (ALI), there were no serious adverse events that were attributable to IC14 and no excess nosocomial infections.

2. Study Hypotheses/Objectives

The primary hypothesis is that inhibiting the CD14 pattern recognition receptor will reduce the intensity of deleterious host inflammatory responses to the SARS-CoV-2 virus and associated tissue damage and improve outcomes in patients with COVID-19 illness.

2.1. Primary Objective

Determine the efficacy of IC14, an anti-CD14 chimeric monoclonal antibody, in patients hospitalized with respiratory disease and hypoxemia due to SARS-CoV-2, in terms of improving the time to resolution of disease using the Eight-Point ordinal scale (Appendix C).

2.2. Secondary Objectives

1. Determine the efficacy of IC14 in reducing the severity of respiratory disease in patients hospitalized with respiratory disease due to SARS-CoV-2.
2. Determine the safety of IC14 in patients hospitalized with respiratory disease due to SARS-CoV-2.

2.3 Exploratory Objectives

1. Determine whether IC14 reduces markers of systemic inflammation in participants hospitalized with respiratory disease due to SARS-CoV-2.

[figure not shown]
2. Determine whether IC14 increases the proportion of participants experiencing clearance of detectable SARS-CoV-2 in nasopharyngeal specimens.

3. Study Design

This is a randomized, double-blind, placebo-controlled study of IC14 (Figure 2 below). Patients hospitalized with pulmonary manifestations of SARS-CoV-2 infection will be randomized to treatment with intravenous IC14 at a dosage of 4 mg/kg on Day 1, then 2 mg/kg once daily on Days 2, 3, 4 or identical-appearing placebo. Study participation will be for a total of 60 days.

The screening window for eligibility will begin at the time of hospital admission. Once screening shows a patient may be eligible, they will be approached for consent. After consent is obtained, if necessary, a pregnancy test will be obtained to complete screening procedures and finalize eligibility. Baseline assessments, consenting and randomization should occur within 24 hours after meeting inclusion criteria and the first administration of study drug should occur as soon as possible within 12 hours after randomization. Study Days are defined as consecutive calendar days beginning from the start of the first study drug administration (Day 1). Study drug should be administered at approximately 24-hr intervals beginning from the start time of the first study drug administration (Day 1). Study participants will not be pretreated with antihistamines or steroids prior to infusion of study drug because of the rarity of infusion reactions in clinical studies with IC14 (e.g. one infusion reaction in 168 participants treated to date). However, if three or more infusion reactions occur during the study that are thought to be related to the study drug, consideration will be given to pretreating all subsequent participants with an antihistamine prior to infusion of the study drug.

Figure 2. Study Design

3.1. Primary Endpoint

The Primary Endpoint is time to clinical recovery, defined as time from baseline to the first day that a participant is in categories 1, 2, or 3 on the Eight-Point Ordinal Scale (below and Appendix C) through Day 28. The Eight-Point Ordinal Scale is an assessment of the clinical status on each study day. The Scale is defined as follows:

- 1) Not hospitalized, no limitations on activities
- 2) Not hospitalized, limitation on activities and/or requiring home oxygen
- 3) Hospitalized, not requiring supplemental oxygen—no longer requires ongoing medical care

- 4) Hospitalized, not requiring supplemental oxygen—requiring ongoing medical care (COVID-19-related or otherwise)
- 5) Hospitalized, requiring supplemental oxygen
- 6) Hospitalized, on non-invasive ventilation or high-flow oxygen devices
- 7) Hospitalized, on invasive mechanical ventilation or extracorporeal membrane oxygenation (ECMO)
- 8) Death

3.2. Secondary Endpoints

3.2.1. Secondary efficacy endpoints:

1. Days-alive-and-free of any episodes of acute respiratory failure through Day-28 defined by need for the following oxygen delivery resources:
 - a. High-flow nasal cannula (flow rates \geq 30L/min with $\text{FiO}_2 \geq 0.4$)
 - b. Noninvasive positive-pressure ventilation through nasal or face mask, or nasal plugs
 - c. Endotracheal intubation and mechanical ventilation
 - d. Extracorporeal membrane oxygenation
2. Mean change in the ordinal scale from baseline to Days 14 and 28.
3. Ordinal scale value on Day 14.
4. All-cause mortality through Days 28 and 60.
5. Proportion of participants alive-and-free of any episode of acute respiratory failure through Day 28.
6. Days-alive-and-free of invasive mechanical ventilation through Day 28.
7. Proportion of participants alive-and-free of invasive mechanical ventilation through Day 28.
8. Proportion of participants alive and discharged from the hospital through Day 28.
9. Proportion of participants who begin corticosteroid therapy for worsening COVID-19 illness after randomization.

3.2.2. Secondary safety endpoints:

1. Safety of IC14 as measured by change from baseline in liver (alanine transaminase, aspartate transaminase, total bilirubin), renal (creatinine), hematological (hemoglobin, white blood cell count with differential), and coagulation function (platelets, prothrombin time) through Day 28.
2. Cumulative incidence of Grade 3 and 4 clinical and/or laboratory adverse events through Day 28.
3. Cumulative incidence of serious adverse events through Day 60.

3.3. Exploratory Endpoints

1. Change from baseline in pro-inflammatory cytokines and other biomarkers in blood on Days 5, 7, 14 and 21.
2. Change in Sequential Organ Failure Assessment (SOFA) score from baseline to Days 5, 7, 14, 21 and 28.
3. Worst SOFA score from baseline to Day 28.
4. Time from baseline to improvement in one category using an ordinal scale through Day 28.
5. Time from baseline to improvement in two categories using an ordinal scale through Day 28.
6. Proportion of participants with negative nasal swabs for SARS CoV2 virus on Days 7 and 14, or at discharge if prior to Day 14.

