8.3. Study Visits or Study Assessments

8.3.1. Baseline – may be done on Study Day 1 Pre-Treatment

The following procedures must be performed, or samples must be collected, prior to study drug administration and within 24 hours of determining eligibility:

- Document reason for hospital admission.
- Document whether medical care is provided under conventional, contingency, or crisis standards of care.
- Physical examination.
- Record vital signs (height, weight, blood pressure, respiratory rate, heart rate and temperature).
- Record variables for Sequential Organ Failure Assessment score (SOFA; Appendix A).
- Determine and record Eight-Point Ordinal Scale (Appendix C).
- Draw the following clinical labs if not collected as part of clinical care: Complete blood count (hematocrit/hemoglobin, platelet count, white blood cell count with differential), PT/INR/PTT, Complete metabolic

panel (serum sodium, bicarbonate, potassium, blood urea nitrogen, creatinine, AST, ALT, alkaline phosphatase, total bilirubin), ferritin, CRP, LDH, D-dimer.

- Collect blood for study labs (15 ml blood)
 - Process and freeze (-80°C) serum for anti-drug antibodies.
 - Process and freeze (-80°C) serum for IC14 PK measurement (to be collected on 40 participants)
 - Process plasma specimens for prognostic biomarkers.
 - Collect nasal swab for viral detection.

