8.3.2. Study Day 1 – Treatment and Post-Treatment

- Administer study drug over 2 hours. The participant should be monitored during infusion and for 1 hour following infusion. Document any interruption of study drug infusion during administration.
- Administer remdesivir 200 mg IV loading dose.
- Collect blood for study labs
 - Process and freeze (-80°C) serum for IC14 PK measurement approximately 1 hour after dosing is completed (to be collected on 40 participants)
- Record vital signs (blood pressure, respiratory rate, heart rate, and temperature) approximately 30 and 60 min after completion of study drug.
- Record variables for Sequential Organ Failure Assessment score (SOFA; Appendix A)
- Determine and record Eight-Point Ordinal Scale performed twice daily as close as possible to 8:00 a.m. and 8:00 p.m. (Appendix C)
- After completion of study infusion, complete the following evaluations in Section 8.3.3..

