 - Collect fresh whole blood for CD14 receptor occupancy determination (PD assessment) (to be collected from 30 participants at selected sites).
- Collect nasal swab for viral detection.
- Administer study drug over 2 hours. The participant should be monitored during infusion and for 1 hour following infusion. Document any interruption of study drug infusion during administration.

- Administer remdesivir 100 mg IV.

8.3.7. Study Day 5

- Conduct all study evaluations in Section 8.3.3, Daily Evaluations While Hospitalized.
- Determine and record Eight-Point Ordinal Scale performed twice daily as close as possible to 8:00 a.m and 8:00 p.m. (Appendix C)
- Record variables for Sequential Organ Failure Assessment score (SOFA; Appendix A).
- Collect blood for study labs
 - Process and freeze (-80°C) serum for PK at approximately 8:00 am (40 participants).
- Administer remdesivir 100 mg IV.

8.3.8. Study Day 7 (if hospitalized) Conduct all study evaluations in Section 8.3.3, Daily Evaluations While Hospitalized.

- Determine and record Eight-Point Ordinal Scale performed twice daily as close as possible to 8:00 a.m and 8:00 p.m. (Appendix C).
- Record variables for Sequential Organ Failure Assessment score (SOFA; Appendix A).
- Draw the following labs if not collected as part of clinical care (values closest to 8:00 a.m. on study day):
Complete blood count (hematocrit/hemoglobin, platelet count, white blood cell count with differential), PT/INR/PTT, Complete metabolic panel (serum sodium, bicarbonate, potassium, blood urea nitrogen, creatinine, AST, ALT, alkaline phosphatase, total bilirubin), ferritin, CRP, LDH, D-dimer If not still hospitalized record the most recent lab values.
- Collect blood for study labs, if still hospitalized
 - Process and freeze (-80°C) serum for PK. (40 participants)
 - Process and freeze (-80°C) plasma for prognostic biomarkers.
 - Collect fresh whole blood for CD14 receptor occupancy determination (PD assessment) (to be collected from 30 participants at selected sites).
- Collect nasal swab for viral detection.

8.3.9. Study Day 14 (if hospitalized or if patient has been discharged prior to this visit conduct a phone call to collect the Eight-Point Ordinal Scale and AE's) Conduct all study evaluations in Section 8.3.3, Daily Evaluations While Hospitalized.

- Determine and record Eight-Point Ordinal Scale performed twice daily as close as possible to 8:00 a.m and 8:00 p.m. (Appendix C).

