- Record variables for Sequential Organ Failure Assessment score (SOFA; Appendix A).
- Draw the following labs if not collected as part of clinical care (values closest to 8:00 am on study day):
Complete blood count (hematocrit/hemoglobin, platelet count, white blood cell count with differential), PT/INR/PTT, Complete metabolic panel (serum sodium, bicarbonate, potassium, blood urea nitrogen, creatinine, AST, ALT, alkaline phosphatase, total bilirubin), ferritin, CRP, LDH, D-dimer. If not still hospitalized record the most recent lab values.
- Collect blood for study labs, if still hospitalized
 - Process and freeze (-80°C) plasma for prognostic biomarkers.
 - Process and freeze (-80°C) serum for PK. (40 participants)
- Collect nasal swab for viral detection.

8.3.10. Study Day 21 (if hospitalized) Conduct all study evaluations in Section 8.3.3, Daily Evaluations While Hospitalized.

- Determine and record Eight-Point Ordinal Scale performed twice daily as close as possible to 8:00 a.m and 8:00 p.m. (Appendix C).
- Record variables for Sequential Organ Failure Assessment score (SOFA; Appendix A).
- Draw the following labs if not collected as part of clinical care (values closest to 8:00 am on study day): Complete blood count (hematocrit/hemoglobin, platelet count, white blood cell count with differential), PT/INR/PTT, Complete metabolic panel (serum sodium, bicarbonate, potassium, blood urea nitrogen, creatinine, AST, ALT, alkaline phosphatase, total bilirubin), ferritin, CRP, LDH, D-dimer. If not still hospitalized record the most recent lab values.
- Collect blood for study labs, if still hospitalized
 - Process and freeze (-80°C) plasma for prognostic biomarkers

8.3.11. Study Day 28

It is preferred that this visit is in person to obtain safety laboratory tests as well as clinical outcome data. However, infection control or other restrictions may limit the ability of the participant to return to the clinic. In this case, the visit may be conducted by phone or virtually, and only clinical data will be obtained. All participants will undergo an ocular examination. This examination will be scheduled as a separate in-person visit, usually in the ophthalmology clinic. This visit should be completed at 28 +/- 1 day to obtain the Eight-Point Ordinal Scale and survival. Chest x-ray and labs should be obtained at this visit or as soon as possible after the visit.

- Record adverse events.

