13.8.2. Analysis of Primary Endpoint

The primary endpoint is time to event (recovery defined above). Study participants who die before day 28 will be assigned the worst time to recovery (28 days); if data are analyzed while some participants are still in follow-up, the Fine-Gray approach to censoring deaths will be used (that is, participants who die will be censored based on time since randomization, with a maximum of 28 days). (Fine and Gray, 1999)

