13.8.6. Missing Data

The study is an in-hospital study, so missing data will be unusual. Every effort will be made to minimize missing follow-up data. For patients who do not return for Day 28 and Day 60 visits, vital status on Day 60 will be ascertained by telephone calls to the subject or relatives, or via death records, or by other available means. A sensitivity analyses with missing

endpoints imputed under conservative assumptions will be conducted to assess their effect. These sensitivity analyses will be specified in the SAP.

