Appendix A: Sequential Organ Failure Assessment (SOFA) Score

Appendix B: Glasgow Coma Scale (GCS)

Appendix C. Eight-Point Ordinal Scale

Appendix D. EQ5D Instrument

Appendix E. Child Pugh Score

Appendix A: Sequential Organ Failure Assessment (SOFA)

Record the worst value in the previous 24 hours:

PaO_2 mm Hg

FiO_2^* %

Respiratory system

PaO₂/FiO₂ [mmHg (kPa)]	SOFA Score
Greater than or equal to 400 (53.3)	0
Less than 400 (53.3)	+1
Less than 300 (40.0)	+2
Less than 200 (26.7) and mechanically ventilated	+3
Less than 100 (13.3) and mechanically ventilated	+4

Nervous system (See appendix D)

Glasgow coma scale	SOFA Score
15	0
13-14	+1
10-12	+2
6-9	+3
Less than 6	+4

Cardiovascular system

Mean arterial pressure OR administration of vasoactive agents required (Listed doses are in units of mcg/kg/min)	SOFA Score
No hypotension	0
MAP less than 70 mmHg	+1
DOPamine less than or equal to 5 or DOBUTamine (any dose)	+2
DOPamine greater than 5, EPINEPHrine less than or equal to 0.1, or norEPINEPHrine less than or equal to 0.1	+3
DOPamine greater than 15, EPINEPHrine greater than 0.1, or norEPINEPHrine greater than 0.1	+4

Liver

Bilirubin, mg/dL ($\mu\text{mol/L}$)	SOFA Score
1.2 - 1.9 (20-32)	+1
2.0 - 5.9 (33-101)	+2
6.0 – 11.9 (102-204)	+3
Greater than or equal to 12.0	+4

Coagulation

Platelets, $\times 10^3/\mu\text{L}$	SOFA Score
Greater than or equal to 150	0
100-149	+1
50-99	+2
20-49	+3
Less than 20	+4

Kidneys

Creatinine, mg/dL ($\mu\text{mol/L}$) (or urine output, UOP)	SOFA Score
Less than 1.2 (less than 110)	0
1.2 - 1.9 (110-170)	+1

2.0 - 3.4 (171-299)	+2
3.5 - 4.9 (300-440) or UOP less than 500 mL per day	+3
Greater than or equal to 5.0 (greater than 440) or UOP less than 200 mL per day	+4

*Estimating FiO_2 from oxygen flow/delivery rates:

Type of O_2 delivery	Flow rates, L/min	FiO_2
Nasal Cannula		~4% FiO_2 added above room air** per 1 L/min
	Room Air	21%
	1 liter per minute	25%
	2 liters per minute	29%
	3 liters per minute	33%
	4 liters per minute	37%
	5 liters per minute	41%
	6 liters per minute	45%
Simple face mask	~6-12 liters per minute	35-60%**
Non-rebreather mask	10-15 liters per minute	~70-90%
High-flow nasal cannula	Up to 60 liters per minute	30-100%

**Varies based on respiratory rate and minute ventilation.

Even though it is calculated sequentially based on the worst values in the past 24 hours, the SOFA Score is not meant to indicate the success or failure of interventions or to influence medical management.

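### Worst SOFA to Day 28 (exploratory endpoint 3) counts the pre-treatment score and gives death no value, so a death can rank better than a ventilated survivor

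*Combined protocol and SAP*

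**What the plan says.** Sections 3.3 and 13.2.4 of the combined protocol and SAP define the endpoint identically: "Worst SOFA score from baseline to Day 28". Neither says whether the baseline score itself counts.

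- **Baseline.** Section 8.3.1 includes SOFA among procedures under this condition: "The following procedures must be performed, or samples must be collected, prior to study drug administration and within 24 hours of determining eligibility".
- **Look-back.** Appendix A instructs: "Record the worst value in the previous 24 hours". The Day 1 score (Section 8.3.2) can therefore draw on hours before the first infusion.
- **Later scores.** The visit lists in Section 8.3 put SOFA on Days 4, 5, 7, 14 and 21. Participants who have gone home do not contribute later scores; the Day 14 telephone contact, for example, covers the ordinal scale and adverse events. SOFA is not listed for Day 2 or 3, among the daily evaluations (8.3.3), or for Day 28 (8.3.11), although exploratory endpoint 2 needs a Day 28 value.
- **Death.** Appendix A has no score for death. The rule in Section 13.8.2 covers the primary endpoint only: "Study participants who die before day 28 will be assigned the worst time to recovery (28 days"). Section 13.8.6 promises a sensitivity analysis with missing "endpoints imputed under conservative assumptions will be conducted to assess their effect", leaves the details to the SAP, and mentions neither SOFA nor death.
- **Test.** Section 13.8.3 compares continuous endpoints by the Wilcoxon rank sum test and names no adjustment for baseline SOFA.

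**The concern.** A worst-score endpoint should rank participants by how badly organ function failed after treatment began. Two features work against that.

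First, death is unscored and SOFA is sparse after Day 7. Someone who declines and dies between visits contributes only the scores recorded before the decline. Dying early also means fewer scores over which to take a maximum. An arm with more deaths could therefore look better on this endpoint.

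Second, the maximum can simply return the pre-treatment score. That carries baseline severity into the outcome, creates ties and blurs any difference between arms.

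**Working it through.** **1. Check the recovery model, since step 2 uses it.** No figure is stated for the SOFA endpoint. Section 13.11 gives Weibull recovery times with shape 0.73, a placebo median of 6 days and a rate ratio (RR) of 1.4; 80% power; type I error 0.05 (taken as two-sided). Allocation is 1:1.

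- Events (Schoenfeld): 4 × (1.960 + 0.842)² / (ln 1.4)² = 277.3, rounded up to 278. The plan states 278.
- Recovered by Day 28: 1 − exp[−RR × ln 2 × (28/6)^0.73] = 0.882 (placebo) and 0.950 (IC14). The plan states the same.
- Participants: 277.3 / 0.916 ≈ 303, or 304 from 278 events. The plan states 302.

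The model is reproduced.

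**2. Who could have only baseline and Day 1 scores?** After Day 1 the next SOFA is on Day 4. With t = 3 days from first dose, (3/6)^0.73 = 0.603:

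- Placebo: 1 − exp(−0.693 × 0.603) = 34%.
- IC14: 1 − exp(−1.4 × 0.693 × 0.603) = 44%.
- For the plan's medians of 7 to 5 days: 31% to 38% (placebo) and 41% to 49% (IC14).

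These are shares recovered. Recovery includes category 3, which is still in hospital, so within the model they are upper bounds on the shares discharged by Day 3.

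**3. How old is the latest SOFA at death?** Take each death day from 2 to 28 and count back to the latest of Days 1, 4, 5, 7, 14 and 21.

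- If a SOFA due on the day of death is obtained, the gap is 2 days or more on Day 3, Days 9–13, Days 16–20 and Days 23–28: 1 + 5 + 5 + 6 = 17 of 27 days (63%). The mean gap is 74/27 = 2.7 days.
- If no SOFA is obtained on the day of death, Days 4, 7, 14 and 21 join the list: 21 of 27 (78%). The mean gap is 94/27 = 3.5 days.
- The longest gap is 7 days either way.

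The percentages apply to deaths only if deaths are spread evenly over these days. With front-loaded deaths (exponential timing, median 5 to 18 days before restriction to Days 2–28), the 63% becomes 41% to 56%, and the 78% becomes 62% to 73%. With a day-of-death SOFA and an even spread within each period, the share is 1/6 for Days 2–7 and 16/21 for Days 8–28. It falls below one half once more than (16/21 − 1/2) / (16/21 − 1/6) = 44% of deaths occur in Days 2–7.

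**4. Effect on ranks (invented scores, for illustration).** Participant B has baseline 3 and Day 7 score 5, declines on Day 9 and dies on Day 11: worst score 5. Participant C has baseline 3, is ventilated with a Day 7 score of 8, and survives: worst score 8. The Wilcoxon test ranks the death as the better outcome.

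**The case against.** - **The phrase can be read as a time origin.** Section 3.1 measures the primary endpoint from baseline and Section 13.2.1 restates it as from the first dose. A post-dose window is a fair reading here too. The text should still say which applies, and this does not settle the scoring of deaths.
- **Worst equal to baseline can be a good result.** Section 1.1 aims to prevent progression, so staying at baseline instead of rising is one way benefit shows. This stands. A reader might infer that such values cannot respond to treatment; the documents do not support that. The Day 1 score is also listed under treatment and post-treatment, so it can exceed baseline.
- **A maximum takes the highest recorded score, not the latest.** This stands. The gaps in step 3 show how long a decline could go unrecorded, not the size of any scoring error.
- **Deaths are visible elsewhere.** Mortality, days alive and free of respiratory failure, and the ordinal scale with death as category 8 all rank above this endpoint. This limits the harm but does not repair the endpoint.
- **Daily data exist.** Blood pressure, oxygen support and clinically drawn laboratory values are recorded daily in hospital (8.3.3), so a partial SOFA could be rebuilt. No section asks for this, and the coma score has no explicit daily record.
- **A rule may sit in a separate SAP.** The protocol defers details to one and no such separate text is available here. If it has a rule for death, that part of the point is met.

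**Conclusion.** The point holds as a minor matter of definition. The mis-ranking of deaths is the substantive part: it can bias the comparison if mortality differs between arms. Including baseline is symmetric between randomized arms, so it adds ties and dilutes a difference but does not bias it.

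The sizes are conditional. The 63% (or 78%) assumes an even spread of deaths over Days 2–28. A reader might infer that most deaths are scored from a visit days earlier; the documents give no death timing, and the share runs from 41% to 78% over the assumptions tried. The 34% and 44% rest on the plan's recovery model and are upper bounds on early discharge. The documents give no SOFA trajectories, so the share of participants whose worst score is simply the baseline value cannot be calculated.

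The endpoint is exploratory. The primary analysis, alpha and sample size are unaffected.

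**What to change.** In Sections 3.3 and 13.2.4 and in the SAP, before unblinding:

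1. Define the endpoint as the worst SOFA recorded after the first dose through Day 28, with death by Day 28 ranked worst. Either a worst-rank rule or the Appendix A maximum (6 organ systems × 4 = 24) would do.
2. Compare arms with a rank-based or proportional-odds model adjusted for baseline SOFA.
3. For those discharged alive before Day 4, use the post-dose Day 1 score. It still reaches back before dosing, so the baseline covariate is needed to absorb that content.
4. Apply the same death ranking to the change-in-SOFA endpoint.
5. State that the last scheduled score is Day 21, or add SOFA to the Day 28 list.

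Items 1 to 4 change wording only and need no new data; adding a Day 28 SOFA under item 5 would need one more assessment. The price is that the score becomes a composite of organ dysfunction and mortality, so a secondary summary in survivors should be shown beside it.
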